11.1 Adverse Event Characteristics and Definitions

11.1.1 Definition of an AE

Any untoward medical occurrence in a subject or clinical investigation subject, temporally associated with the use of a medicinal product, whether or not considered related to the medicinal product.

Note: An AE can therefore be any unfavorable and unintended sign (including an abnormal laboratory finding), symptom, or disease (new or exacerbated) temporally associated with the use of a medicinal product. For marketed medicinal products, this also includes failure to produce expected benefits, abuse, or misuse. Examples of events meeting the definition of an AE include:

- Exacerbation of a chronic or intermittent pre-existing condition including either an increase in frequency and/or grade of the condition
- New conditions detected or diagnosed after study treatment administration even though it may have been present prior to the start of the study
- Signs, symptoms, or the clinical sequelae of a suspected interaction
- Signs, symptoms, or the clinical sequelae of a suspected overdose of either study treatment or a concomitant medication (overdose per se will not be reported as an AE/SAE).

Events that do not meet the definition of an AE include:

- Medical or surgical procedure (e.g., endoscopy, appendectomy); the condition that leads to the procedure is an AE.
- Situations where an untoward medical occurrence did not occur (social and/or convenience admission to a hospital).
- Anticipated day-to-day fluctuations of pre-existing disease or condition present or detected at the start of the study that do not worsen.
- The disease/disorder being studied or expected progression, signs, or symptoms of the disease/disorder being studied, unless more severe than expected for the subject's condition.

11.1.2 Definition of a SAE

A serious adverse event is any untoward medical occurrence that, at any dose:

- a. Results in death
- b. Is life-threatening

NOTE: The term 'life-threatening' in the definition of 'serious' refers to an event in which the subject was at risk of death at the time of the event. It does not refer to an event, which hypothetically might have caused death, if it were more severe.

c. Requires hospitalization or prolongation of existing hospitalization

NOTE: In general, hospitalization signifies that the subject has been detained (usually involving at least an overnight stay) at the hospital or emergency ward for observation and/or treatment that would not have been appropriate in the physician's office or outpatient setting. Complications that occur during hospitalization are AEs. If a complication prolongs hospitalization or fulfills any other serious criteria, the event is

serious. When in doubt as to whether "hospitalization" occurred or was necessary, the AE should be considered serious.

Hospitalization for elective treatment of a pre-existing condition that did not worsen from baseline is not considered an SAE.

d. Results in disability/incapacity, or

NOTE: The term disability means a substantial disruption of a person's ability to conduct normal life functions. This definition is not intended to include experiences of relatively minor medical significance such as uncomplicated headache, nausea, vomiting, diarrhea, influenza, and accidental trauma (e.g. sprained ankle) which may interfere or prevent everyday life functions but do not constitute a substantial disruption.

- e. Is a congenital anomaly/birth defect.
- f. All grade 4 laboratory abnormalities
- g. Specific liver function abnormalities and pregnancy

Medical or scientific judgment should be exercised in deciding whether reporting is appropriate in other situations, such as important medical events that may not be immediately life-threatening or result in death or hospitalization but may jeopardize the subject or may require medical or surgical intervention to prevent one of the other outcomes listed in the above definition. These should also be considered serious. Examples of such events are invasive or malignant cancers, intensive treatment in an emergency room or at home for allergic bronchospasm, blood dyscrasias or convulsions that do not result in hospitalization, or development of drug dependency or drug abuse.

11.1.3 Laboratory and Other Safety Assessment Abnormalities Reported as AEs and SAEs

Any abnormal laboratory test results (hematology, clinical chemistry, or urinalysis), or other safety assessments (e.g., ECGs, radiological scans, vital signs measurements) including those that worsen from baseline, and events felt to be clinically significant in the medical and scientific judgment of the investigator are to be recorded as an AE or SAE, in accordance with the definitions provided.

However, any clinically significant safety assessments that are associated with the underlying disease, unless judged by the investigator to be more severe than expected for the subject's condition, are not to be reported as AEs or SAEs.

11.1.4 Disease-Related Events and/or Disease-Related Outcomes Not Qualifying as SAEs

Disease Related Events are events (serious or non-serious) anticipated to occur in the study population due to the underlying disease. These could include overall disease progression or pain or discomfort caused by growing tumors. Such events do not meet the definition of an Adverse Event unless assessed to be more severe than expected for the subject's condition.

An event which is part of the natural course of the disease under study (i.e., disease progression) does not need to be reported as an SAE. Deaths and hospitalizations related to disease (other than for study procedures) during the study period and 30 days after completion must be reported as SAEs.

Disease Related Events that would qualify as an Adverse Event or Serious Adverse Event:

 An event based on the underlying disease that is worse than expected as assessed by the investigator for the subject's condition

The investigator believes there is a causal relationship between the investigational product³³/study treatment/protocol required therapies and disease worsening

11.2 Risks, toxicities and adverse drug reactions - Epacadostat

Epacadostat dosing likely will produce side effects, and not all side effects may be known. Specific identified risks and potential risks are highlighted below, as well as adverse drug reactions observed in clinical trials.

See the investigation brochure for complete list of possible adverse events related to epacadostat.

11.2.1 Identified Risks - Epacadostat

Monotherapy

In the Phase 1 clinical study in subjects with refractory solid tumors (INCB 24360-101), epacadostat was well tolerated at doses ranging from 50 mg QD to 700 mg BID. Twenty-five (48.1%) of the 52 subjects administered epacadostat had a single SAE. The most frequently reported SAEs were disease progression (4 subjects, 7.7%), followed by abdominal pain, nausea, and hypoxia (3 subjects each, 5.8%). Treatment-emergent adverse events (TEAEs) were reported in all subjects. The most commonly reported treatment-related TEAEs were fatigue and nausea (25 subjects, 48.1%). The incidence and severity of fatigue were not dose-related. Two DLTs occurred: 1 DLT of radiation pneumonitis at the 300 mg dose level and 1 DLT of fatigue at the 400 mg BID dose level.

Data from Study INCB 24360-210 (600 mg BID of epacadostat versus 20 mg BID of tamoxifen in Stage III or IV epithelial ovarian cancer) are available as of the data cutoff on 29 OCT 2014. At the time of the cutoff, 42 subjects were enrolled (22 in the epacadostat-treated group and 20 in the tamoxifen-treated group). Based on the preliminary unaudited data through that date, no subject had an AE leading to death. Two

subjects (4.8%) had an SAE. One SAE was reported in the epacadostat group (abdominal pain), and 1 SAE was reported in the tamoxifen group (ascites). Treatment-emergent AEs were reported in 32 subjects (76.2%) with 17 subjects (77.3%) in the epacadostat group and 15 subjects (75.0%) in the tamoxifen group. Fatigue was the most frequently reported TEAE in the epacadostat group (8 subjects, 36.4%), followed by nausea (6 subjects, 27.3%) and abdominal distention, constipation, and vomiting (4 subjects each, 18.2%). This study has been terminated by Incyte. No new safety concerns with epacadostat were identified.

Combination Therapy

Preliminary data from Study INCB 24360-201 (evaluating the combination of epacadostat and ipilimumab) suggest that epacadostat 50 mg BID is well tolerated with ipilimumab based on evaluation of subjects in 50 mg BID continuous cohort. Only 4 of the 18 evaluable subjects reported DLTs, which included a Grade 3 diarrhea (n = 1), a Grade 3 ALT/AST elevation (n = 1), a Grade 3 colitis (n = 1), and a Grade 3 pneumonitis (n = 1). One of the 9 subjects enrolled in 50 mg BID intermittent cohort reported Grade 3 colitis as a DLT. The most common irAEs with Grade 3 were AST elevation and colitis (n = 4, 9.5% each) and ALT elevation (n = 3, 7.1%). Other irAEs with Grade 3 observed in only 1 subject were idiopathic thrombocytopenic purpura, diarrhea, acute renal failure, pneumonitis, pruritus, and rash (2.4% each). Common treatment emerging AEs reported included fatigue (n = 29, 69%), constipation and nausea (n = 13, 31% each), decreased appetite and headache (n = 11, 26% each), and vomiting (n = 10, 24%). This study is currently closed to enrollment.

The initial evaluation of epacadostat 300 mg BID in combination with ipilimumab was terminated because of the occurrence of Grade 3 or 4 alanine aminotransferase (ALT)/aspartate aminotransferase (AST) elevation in 5 of 7 subjects treated at this dose. The most common Grade 1 or 2 AEs reported at 25 mg BID (N = 8) were fatigue (n = 6, 75%), abdominal pain (n = 6, 75%), headache (n = 5, 62.5%), rash (n = 4, 50%), nausea (n = 4, 50%), cough (n = 4, 50%), and diarrhea (n = 3, 37.5%). Grade 3 or 4 AEs that occurred in > 1 subject at 25 mg BID were colitis (Grade 3) and elevated alkaline phosphatase (Grade 3), with n = 2 each (25%).

As of the data cut off (28 MAR 2016), 60 subjects have been enrolled in INCB 24360-202 (epacadostat 25 mg, 50 mg, 100 mg, and 300 mg BID in combination with pembrolizumab). Based on the preliminary unaudited safety data (unaudited), no Grade 4 treatment related AEs were reported. Three subjects (5%) discontinued for a treatment-related AE: Grade 3 arthralgia, Grade 3 AST elevation, and Grade 2 nervous system disorder. No treatment-related deaths occurred. Treatment-emergent AEs were reported in 44 subjects (73.0%). The most frequently reported AEs were rash (27%) followed by fatigue (23%). Rash includes the preferred terms rash, rash generalized, rash maculopapular, rash pruritic, and rash follicular. As of the data cutoff (28 MAR 2016), 18 subjects in the Phase 1 portion of the INCB 24360-202 study and 119 subjects in the Phase 2 portion of the study have received combination treatment with pembrolizumab and the 100 mg BID dose of epacadostat, the recommended dose for the Phase 3 study. The data for Phase 2 presents a subset of 99 subjects who had at least 1 month of safety data. The most frequently reported (15%) AEs of any grade for the combined Phase 1

and Phase 2 subjects treated with epacadostat 100 mg BID were fatigue (35.0%), constipation (24.8%), diarrhea (20.5%), nausea (20.5%), vomiting (18.8%), pyrexia (16.2%), and dyspnea (15.4%). Fatigue (13.7%) and rash (11.1%; including the preferred terms rash, rash maculopapular, rash generalized, and rash macular) were the only treatment-related AEs reported in > 10% of subjects. Treatment-related AEs of rash were only reported in Phase 2. Treatment-related AEs 2: Grade 3 occurring in more than 1 subject who received epacadostat 100 mg BID in Phase 1 or Phase 2 included rash (5 subjects, 4.3%) and dehydration, lipase increased, AST increased, and nausea (2 subjects [1.7%] each). Theoretically, inhibition of IDO1 could cause an increase in serotonin levels that could precipitate a cluster of AEs termed serotonin syndrome (SS) when administered alone or in combination with other serotonergic agents. This rare syndrome has been associated with some monoamine oxidase inhibitors (MAOIs) and combinations of serotonergic drugs. The clinical manifestations of SS range from barely perceptible to lethal; onset is rapid (within 12 hours of drug[s] administration). Based on preliminary studies in the rat, concentrations of epacadostat in the cerebrospinal fluid were below the quantifiable limit of detection (2 nM) after IV dosing, and total brain homogenate concentrations were approximately 15% of corresponding plasma concentrations. Therefore, epacadostat exhibits apparent limited penetration across the blood-brain barrier and is likely not associated with significant effects on tryptophan metabolism in the brain that might affect brain serotonin levels. In the INCB 24360-201 study, 12 of the 48 subjects enrolled as of 29 OCT 2014 received concomitant treatment with an SSRI and epacadostat, and O of 12 subjects exhibited SS. Although this represents a hypothetical risk only and has not been observed in clinical studies of epacadostat, use of MAOIs will be prohibited during the study, and all subjects will be assessed for SS symptoms at an appropriate timeframe after dose administration. Subjects will be provided with an informative subject leaflet describing the signs and symptoms of the syndrome along with instructions to seek immediate medical care if any of these signs or symptoms is observed.

Risk: Serotonin Syndrome

Procedure for Subjects Exhibiting Serotonin Syndrome

There is a theoretical chance that epacadostat could cause an increase in serotonin levels in the brain that might trigger SS (http://www.nejm.org/doi/full/10.1056/NEJMra041867) when administered in combination with other serotonergic agents. This syndrome has been most closely associated with use of MAOIs, Demerol®, linezolid, or methylene blue; all of these agents are prohibited during the study. Selective serotonin reuptake inhibitors (SSRIs) and serotonin/norepinephrine reuptake inhibitors (SNRIs) are permitted in the study. The following procedures will be implemented if subjects exhibit the signs/symptoms of SS described in Table 6, including tremor; hyperreflexia; and spontaneous, ocular, or inducible clonus, together with agitation, fever, diaphoresis, or muscle rigidity:

 Immediately interrupt epacadostat administration. Administration of pembrolizumab may continue.

- Immediately interrupt any SSRI or SNRI administration.
- Provide appropriate medical management of the subject until all signs/symptoms are resolved (eg, IV fluids and/or sympathomimetic amines for hypotension, benzodiazepines for agitation, administration of 5-hydroxytryptamine antagonists, such as cyproheptadine).
- If subject chooses to remain in the study, restart treatment with epacadostat after the SSRI or SNRI has been discontinued, no sooner than 5 half-lives have elapsed for the specific SSRI or SNRI in question and after resolution of signs/symptoms of SS. The SSRI or SNRI treatment MAY NOT be restarted.
- If subject chooses to withdraw from the study or must restart treatment with SSRI or SNRI, the subject should be scheduled for a follow-up visit. Treatment with SSRI or SNRI may be initiated 2 weeks after resolution of signs and symptoms of SS.

 Table 6:
 Sign and Symptoms of Serotonin Syndrome

Tremor and hyperreflexia		
Spontaneous clonus		
Muscle rigidity, temperature> 38°C (100.4°F), and either ocular clonus or inducible clonus		
Ocular clonus and either agitation or diaphoresis		
Inducible clonus and either agitation or diaphoresis		

Adverse Drug Reactions - Epacadostat

As of 29 Oct 2016, 898 unique subjects have been exposed to INCB024360 in Incyte sponsored studies as monotherapy (149 subjects) and/or in combination with checkpoint inhibitors (anti-PD-1 targeted therapy [543 subjects]); **PD-L**1-targeted therapy (124 subjects); anti-CTLA-4 targeted therapy (50 subjects); and a JAK inhibitor with JAK1 selectivity (32 subjects).

Table 7. contains a list of expected treatment-emergent adverse events for epacadostat monotherapy

Table 7: Expected Treatment-Emergent Adverse Events for Epacadostat Monotherapy

System. Organ Class MedDRA Preforred Term	OveraU Frequency All Grades N(%}	G1·ad1'3 or Gr:acle 4 N{%)	Frequency of Serious E,,ents N(%>)
Gasfroiotl'sfinal di <jordl't·s< td="">			</jordl't·s<>			
Dianhea	Very common -19 (128)	-	-
Nausea	Very common- 44 (29.5)	Common-5 (3.4)	Connnon 3 (2.0)
Vomiting	Vei:ycommon-27 (18.1)	Common - 4 ,(2.7)	Common - 2 (1.3)
Gen.eraJ dirorde1·s and adminisfration.s	site c,onditions		
Asthenia	Comm.on - 2 (L3)	-	-
Fatigue	Very common- 50 (33_6)	Common - 6 (4.0)	-
lnves1ti.gatioos			
Al.mine aminotransferase increased	Common - 4 (2.7)	Common - 2 (1.3)	-
Aspartate aminotnmsfense incre.as:ed Common - 4 (2_7)		Uncommon - 1 (0.7)	-
1\{usculoskeletal and c ollD.ectrive tissue	disorders		
Arthralgia	Co:mmon - 6 (4.0)	-	-
Skin and subcutaneous tissue diso rders	S		
Pruritus	Common - 4 (2_7)	-	-
Rash	Common - 5 (3.4)	-	-
Rash maculo-papular	Common - 5 (1.4)	Common - 2 (1.3)	-
Rash papnlar	Common - 2 (1-3)	-	-

[&]quot;-"=:not expected.

Table 8. Expected TEAEs for Epacadostat and Anti-PD-1 Combination Therapy (n=543)

System. Organ Class M:l'dDRA P:n fen:ed Term	Overall F1-equency All Grades - (%)	Grade 3 or G1·ade 4 (%)	Fn:iquency of Serious Events - (%)	
Endocrine cli.sm·der:s				
Adcenal insufficiency	Unco.mmon-2 (0.4)	Uncomm.011- I (0.2)	-	
Hypothyroidism	Common-16 (4.8)	-	-	
G3sh·ointestinal disorders				
DiMrhea	Verycommon-103 (19.0)	Common - 8 (1.5)	Uncommon - 4 (0.7)	
Nausea	VeryCOIIIIIIOII- 145(26.7)	Common - 9 (1.7)	Comm.on-13 (2.4)	
Vomiting	Veryaommon-101 (l&.6)	Common-10 (L&)	Common - 9 (L 7)	
GeneraJ disordea·s and 3 dminisjration site conditions				
Astheni.a	Comwon-31 (:'.i7)	Common- 7 (1.3)	Common- 6(1.1)	
Fatigue	Veryaommon-230 (42.4)	Common-11 (20)	Uncommon - 5,(0.9)	

System Organ Class MedDRA Preferred Term	Overall Frequency All Grades N (%)	Grade 3 or Grade 4 N (%)	Frequency of Serious Events N (%)
Investigations		5	
Alanine aminotransferase increased	Common – 47 (8.7)	Common – 8 (1.5)	123
Aspartate aminotransferase increased	Very common – 56 (10.3)	Common – 9 (1.7)	=
Musculoskeletal and connective	tissue disorders		ne.
Arthralgia	Very common - 60 (11.1)	Uncommon - 3 (0.6)	_
Respiratory, thoracic, and media	astinal disorders	3	ők pe
Pneumonitis	Uncommon - 5 (0.9)	Uncommon - 1 (0.2)	Uncommon - 2 (0.4)
Skin and subcutaneous tissue dis	sorders		25
Pruritus	Very common - 72 (13.3)	Uncommon - 3 (0.6)	_
Pruritus generalized	Common - 7 (1.3)	100	=
Rash	Very common - 86 (15.8)	Common - 16 (2.9)	Uncommon - 2 (0.4)
Rash generalized	Common - 13 (2.4)	Uncommon - 2 (0.4)	=
Rash macular	Uncommon - 3 (0.6)	Uncommon - 2 (0.4)	
Rash maculo-papular	Common - 37 (6.8)	Common - 20 (3.7)	Uncommon - 4 (0.7)
Rash papular	Uncommon - 5 (0.9)		=
Rash pruritic	Common - 10 (1.8)	Uncommon - 1 (0.2)	_
Rash pustular Uncommon – 2 (0.4)		pa	=

[&]quot;-" = not expected.

Preliminary safety results for the phase I study INCB 24360-202, of epacadostat in combination with pembrolizumab) were presented in a poster presentation and are presented in Table 9; these data have a data cutoff of 07 JUL 2016.⁵⁰ Phase 1 has completed enrollment with a total of 62 subjects. Subjects were treated with epacadostat 25 mg BID (n = 4), 50 mg BID (n = 20), 100 mg BID (n = 18), and 300 mg BID (n = 20) in combination with pembrolizumab 2 mg/kg or 200 mg IV every 3 weeks. Treatment-related AEs were reported in 50 subjects (81%). Table 9 presents treatment-related AEs 5% or Grade 3/4 AEs in 1 subject in the Phase 1 portion of the study. The most frequently reported treatment-related AEs were fatigue and rash (29% each). Rash includes the preferred terms rash, rash erythematous, rash generalized, rash maculo-papular, rash pruritic, and rash follicular. The most frequently reported Grade 3 treatment-related AE was rash (8%).

Five subjects (8%) discontinued for a treatment-related AE: Grade 3 arthralgia, Grade 3 AST increased/Grade 2 ALT increased, Grade 3 lipase increased, Grade 3 aseptic meningitis, and Grade 2 nervous system disorder. No treatment-related deaths occurred as of 07 JUL 2016.

Table 9: Related TEAEs 5% or Grade 3 / 4 TEAEs in 1 subject in the phase I population in study INCB 24360-202

Adverse Event, n (%)	All Grades (N = 62)	≥ Grade 3 (N = 62)
Total	50 (81)	12 (19)
Fatigue	18 (29)	0 (0)
Rash ^a	18 (29)	5 (8)
Pruritus ^b	14 (23)	0 (0)
Arthralgia	12 (19)	1 (2)
Diarrhea	11 (18)	0 (0)
Nausea	10 (16)	1 (2)
Pyrexia	7 (11)	0 (0)
Vomiting	7 (11)	1 (2)
AST increased	5 (8)	1 (2)
Chills	5 (8)	0 (0)
Dizziness	5 (8)	0 (0)
Myalgia	5 (8)	0 (0)
Constipation	4 (6)	0 (0)
Headache	4 (6)	1 (2)
Lipase increased	3 (5)	3 (5)
Amylase increased	2 (3)	2 (3)
Anxiety	2(3)	1 (2)
Mucosal inflammation	2 (3)	1 (2)
Meningitis aseptic	1 (2)	1 (2)

AE = adverse event; AST = aspartate aminotransferase.

The combination of epacadostat and pembrolizumab is under investigation in the setting of melanoma, in a phase III study, INCB 24360-301. The recommended phase III dose for this study was based on findings from phase I and phase II of study INCB 24360-202. The preliminary safety results summarized below are the basis for the initial recommended dose in melanoma of epacadostat 100 mg BID in combination with pembrolizumab 200 mg IV Q3W; these data have a data cutoff of 28 MAR 2016.

Eighteen subjects in the Phase 1 portion of the study and 119 subjects in the Phase 2 portion of the study have received at least 1 dose of combination treatment with pembrolizumab and the 100 mg BID dose of epacadostat. The data for Phase 2 provides a subset of 99 subjects who had at least 1 month of safety data. Subjects were included in the data presented below if they were enrolled and received at least 1 dose of study medications on or before 28 FEB 2016 with a data cutoff of 28 MAR 2016 for all subjects. Of the 119 subjects, 115 had the following cancers: melanoma (n = 7), PD-L1-positive NSCLC (n = 5), PD-L1-negative/indeterminate NSCLC (n = 4), transitional cell carcinoma of the genitourinary tract (n = 21), TNBC (n = 24), ovarian cancer (n = 35), DLBCL (n = 3), and SCCHN (n = 16). At the time of the data cutoff, the disease history information for the 4 remaining subjects had not yet been specified in the database.

^a Rash includes the following MedDRA preferred terms: rash, rash erythematous, rash generalized, rash maculo-papular, rash pruritic, and rash follicular.

^b Pruritus includes the following MedDRA preferred terms: pruritus and pruritus generalized.

Table 10 presents an overall summary of TEAEs for subjects administered epacadostat 100 mg BID in the Phase 1 or Phase 2 cohorts of the study.

Table 10: Summary of Treatment-Emergent Adverse Events in Study INCB 24360-202 (Data Cutoff 28 MAR 2016)

Variable, n (%)	Epacadostat 100 mg BID (Phase 1) ^a (n = 18)	Epacadostat 100 mg BID (Phase 2) (n = 99)	Epacadostat Total 100 mg BID (N = 117)
Number of TEAEs reported	219	570	789
Subjects who had at least 1 TEAE	17 (94.4)	85 (85.9)	102 (87.2)
Subjects who had at least 1 TEAEs ≥ Grade 3	9 (50.0)	30 (30.3)	39 (33.3)
Subjects who had at least 1 treatment-related TEAE	16 (88.9)	46 (46.5)	62 (53.0)
Subjects who had at least 1 treatment-related TEAE ≥ Grade 3	4 (22.2)	15 (15.2)	19 (16.2)
Subjects who had at least 1 SAE	8 (44.4)	19 (19.2)	27 (23.1)

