11.4.1 Epacadostat

Dose reductions/Interruptions - Epacadostat

In some circumstances, it may be necessary to temporarily interrupt both study treatments as a result of AEs that may have an unclear relationship to study drug. If an interruption is necessary both study treatments should be interrupted.

Any interruptions of> 2 weeks or for LFT abnormalities must be discussed with the medical monitor before resuming treatment. Treatment with both study drugs should be withheld for drug-related Grade 4 hematologic toxicities, nonhematological toxicity Grade 3 (including laboratory abnormalities), and severe or life-threatening AEs.

Epacadostat may be dose reduced according to the guidelines and dose levels described in Table 14.

Dosing interruptions may be permitted in the case of medical/surgical events or logistical reasons not related to study therapy (eg, elective surgery, unrelated medical events,

subject vacation, and/or holidays). Subjects will be placed back on study therapy within 3 weeks of the scheduled interruption. The reason for interruption should be documented in the subject's study record.

For patients who do not tolerate the RP2D of epacadostat in combination with pembrolizumab, three dose reductions are permitted (Table 14) in order to allow the patient to continue on study drug. The following guidelines need to be applied and these changes must be recorded on the Dosage Administration Record. Please refer to Table 15 for dose reduction steps and criteria for interruption and re-initiation of epacadostat for drug-related toxicities. Doses held during the study will not be made up. When toxicity that resulted in a dose reduction improves to grade 1 or less, the dose can be re-escalated at the investigators discretion provided there are no other concomitant toxicities.

Table 14 Dose Modification Algorithm for Adverse Events Associated with Epacadostat

Epacadostat Dose Levels	Dose Level 1 (starting dose)	Dose Level -1	Dose Level -2
Actual Dose	100mg bid	50mg bid	25mg bid

Table 15. Dose Modification Guidelines for Epacadostat Related Adverse Effects without Immune Etiology

Toxicity	Grade	Hold	Timing for	Dose for	Discontinue
		Treatment	Treatment	Treatment	Subject (after
		(Y/N)	Restart	Restart	discussion with PI)
Hematologic	1,2,3	No	N/A	N/A	N/A
Toxicity					
	4	Yes	Permanently discontinue treatment	N/A	Permanently discontinue study treatment
Non Hematologic Toxicity	1	No	N/A	N/A	N/A

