Note: Exception to be treated to similar Grade 1 toxicity: -G2 alopecia	2	Consider holding for persistent symptoms	Toxicity resolves to ::;; grade 1 or baseline	Restart at same dose	Toxicity does not resolve within 12 weeks of last dose of treatment
-G2 fatigue	nyestigator agre	ement subjects	Toxicity resolves to ::;; grade 1 or baseline. Subjects with AEs that stabilize at grade 2 (such as neuropathy) may resume treatment upon principal investigator approval. Permanent discontinuation of epacadostat in setting of grade 4 toxicities with the exception of grade 4 laboratory abnormalities that are deemed clinically insignificant	Restart at 1 dose level lower	Toxicity does not resolve within 12 weeks of last dose of treatment. Permanent discontinuation should be considered for any severe or life threatening event.

With principal investigator agreement, subjects with a laboratory AE still at grade 2 after 12 weeks may continue treatment in the study only if asymptomatic and controlled.

Adverse events of a potential immunologic etiology or immune-related AEs (irAEs) may be defined as an AE of unknown etiology, associated with drug exposure and consistent with an immune phenomenon. Immune-related AEs may be predicted based on the nature of the compounds, their mechanism of action, and reported experience with immunotherapies that have a similar mechanism of action. Special attention should be paid to AEs that may

be suggestive of potential irAEs. An irAE can occur shortly after the first dose or several months after the last dose of treatment.

If an irAE is suspected, efforts should be made to rule out neoplastic, infectious, metabolic, toxin, or other etiologic causes prior to labeling an AE as an irAE.

Immune-related adverse events may be attributable to epacadostat alone, pembrolizumab alone, or the combination of both agents. If the event is clearly related to one of the agents, follow the instructions specific for that agent. If the event is related to both agents, follow the action taken instructions for both.

Suggested supportive care measures for the management of adverse events with potential immunologic etiology are outlined in Table 16. below. Note that several courses of steroid tapering may be necessary as symptoms may worsen when the steroid dose is decreased.

It may be necessary to perform conditional procedures such as bronchoscopy, endoscopy, or skin photography as part of evaluation of the event.

 Table 16:

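### For serotonin syndrome judged related to epacadostat, Section 11.2.1 allows restart with no grade limit, Table 15 states permanent discontinuation at grade 4, and neither text is given precedence

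*Combined protocol and SAP*

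**What the plan says.** Two parts of the protocol bear on epacadostat after serotonin syndrome (SS).

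**Section 11.2.1, procedure for subjects exhibiting SS.** The trigger is a pattern of signs, not a CTCAE grade: "The following procedures will be implemented if subjects exhibit the signs/symptoms of SS described in Table 6". Epacadostat and any SSRI or SNRI are interrupted at once and the subject is treated. A subject who elects to stay on study is then to "restart treatment with epacadostat after the SSRI or SNRI has been discontinued, no sooner than 5 half-lives have elapsed" for the agent concerned "and after resolution of signs/symptoms of SS". No grade limit and no restart dose are given. The same section describes the severity range: "The clinical manifestations of SS range from barely perceptible to lethal".

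**Section 11.4.1, Table 15.** The text before the tables sends the reader to Table 15 for dose-reduction steps and for the criteria to interrupt and re-initiate epacadostat after drug-related toxicity. The table is titled "Dose Modification Guidelines for Epacadostat Related Adverse Effects without Immune Etiology". For non-hematologic toxicity it gives:
- grade 1: no hold;
- grade 2: holding is to be considered if symptoms persist, with restart at the same dose;
- the severe row above grade 2: "Restart at 1 dose level lower", and "Permanent discontinuation of epacadostat in setting of grade 4 toxicities with the exception of grade 4 laboratory abnormalities", the exception being limited to laboratory values judged clinically insignificant.

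The last column of the severe row, which applies after discussion with the principal investigator, says only that permanent discontinuation is to be considered for a severe or life-threatening event.

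**The concern.** SS judged related to epacadostat has no immune etiology, so it falls within the title of Table 15 as well as under its own procedure. The protocol's stated severity range reaches lethal events, so grade 4 cases are within the scope of both texts. A site that starts from Section 11.2.1 finds that restart is possible. A site that starts from Section 11.4.1 finds that it is not.

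What is at stake is consistent handling of a rare but potentially life-threatening event, with which no site will have experience. Safety is also a secondary endpoint. Two patients with the same event could be re-exposed or permanently stopped depending on which section was consulted, and the exposure record would carry that difference.

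**Working it through.** No arithmetic applies, because the point rests on no sample size, error rate or event count. The check sets the two texts side by side by grade, for SS judged related to epacadostat.

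1. **Does Table 15 apply?** Section 11.4.1 refers drug-related toxicities to it without listing exceptions, and its title covers epacadostat-related effects of non-immune origin. It has no carve-out for SS. It therefore applies once the event is attributed to epacadostat, and not otherwise.

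2. **Is either text given precedence?** Sections 9, 11 and 13 and Appendix B contain no rule saying that the SS procedure overrides Table 15, or the reverse.

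3. **Comparison by grade:**
   - *Grade 1.* SS procedure: immediate interruption. Table 15: no hold. These differ.
   - *Grade 2.* SS procedure: immediate interruption, no restart dose stated. Table 15: consider holding, restart at the same dose. These are compatible, since Table 15 permits the hold and the procedure does not contradict the dose.
   - *Severe row, below grade 4.* SS procedure: restart after washout and resolution, no dose stated. Table 15: restart one dose level lower. The procedure is silent here, so this is not an opposite instruction.
   - *Grade 4 (not a laboratory abnormality).* SS procedure: restart after washout and resolution. Table 15: permanent discontinuation. These conflict directly.

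4. **How firm is the grade 4 text in Table 15?** One cell states permanent discontinuation. The last cell of the same row says discontinuation is to be considered for severe or life-threatening events. The table is therefore uneven within itself. The softer cell narrows the gap to the SS procedure but does not close it, because the firmer cell still stands.

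5. **Does the reading depend on damaged text?** The grade label of the severe row is missing from the text available. The grade 4 instruction names the grade in its own wording, so the main conflict does not rest on that label.

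**Result:** one direct conflict (grade 4), one minor conflict (the hold at grade 1), one silence (restart dose in the severe row) and no conflict at grade 2.

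**The case against.** The best defence is that an event-specific procedure overrides a general table, particularly one framed as guidelines. The two can also be read together: the procedure adds a washout condition, and Table 15 supplies the grade and dose rules. Joint reading works at grade 2 and in the severe row below grade 4. It cannot settle grade 4 without deciding which text yields, and the protocol does not say. Section 11.4.1 points to Table 15 without an exception.

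A second defence is attribution. Section 11.2.1 presents SS mainly as arising with other serotonergic agents, and causality is assigned event by event under Section 11.6.4. That stands: if an event is attributed wholly to the SSRI or SNRI, Table 15 is not engaged. The conflict is confined to events judged related to epacadostat.

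A third is that other checks limit a restart. Interruptions longer than 2 weeks must be discussed with the medical monitor before resuming, and a physician may withdraw a patient. These reduce the chance of an unconsidered restart, but they do not say which rule the discussion should follow.

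Finally, SS is described as a hypothetical risk not observed in clinical studies of epacadostat. That is correct and limits the size of the point. The response-rate primary endpoint would not plausibly be affected.

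**Conclusion.** The point holds in a narrow form. For SS judged related to epacadostat, the protocol contains two unreconciled rules on restart at grade 4 and a smaller disagreement on the hold at grade 1. The SS procedure is also silent on restart dose where Table 15's severe row gives one. Few or no patients are expected to be affected. The conclusion assumes that the event is attributed to epacadostat and that Table 15 covers it, as its title and the referring sentence indicate.

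Four stronger readings are tempting but not supported:
- A reader might infer opposite instructions at every grade. Grade 2 is compatible, and the severe row below grade 4 meets only silence.
- A reader might infer that the restart rule fails for a patient taking no SSRI or SNRI. In that case the washout condition is simply empty, and resolution of symptoms still applies.
- A reader might infer a monitoring gap from "all subjects will be assessed for SS symptoms at an appropriate timeframe after dose administration", since Table 5 names no SS check. Section 11.2.1 also gives every subject a leaflet on the signs with instructions to seek immediate care, and Table 5 schedules adverse-event review at each treatment visit shown. Together these largely cover the matter.
- A reader might turn the 0 of 12 SSRI users without SS in the ipilimumab combination study into an expected number of cases here. An upper bound from 12 patients mainly reflects how few they are. It would count SS of every grade, and it would ignore the broader statement that SS has not been observed with epacadostat.

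**What to change.** Reconcile the SS procedure in Section 11.2.1 with Table 15. State in one place which text governs interruption and restart of epacadostat after SS, explicitly including grade 4, the hold at grade 1 and the restart dose, and cross-reference it from the other. In the same edit, bring the two grade 4 statements within Table 15's severe row into line as they apply to SS. The clinical team must choose the rule; this review takes no view on which is right.

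The cost is a short protocol clarification, with no new visit, patient or sample. Section 16.3 describes the study as completed. If dosing has ended, the remaining action is to document which rule was applied to any SS case, or that there was none.
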